Human papilloma virus (HPV) is thought to play a significant role in many of these cancers presenting as CUP.[6,7] Smaller or involved primary foci are known to be more common in HPV related cancers which may be contributing to the apparent incidence of these unknown primaries, or occultomas as they may also be called. A histological technique called step serial sectioning (SSS) allows examination of tissue specimens in greater detail than conventional histology. It has not previously been used to investigate the primary site in head and neck cancer but the oropharyngeal tissues that potentially harbour these small primaries make a sensible target to pioneer its usage. It is hypothesised that utilising SSS on tonsillectomy and TBM specimens may increase the identification rate of the primary site and may subsequently affect recommended management.

Currently, we do not understand why some cancers present with cervical metastases with no evident primary site. There has been an explosion in genomics research in many cancers, but this remains an understudied area in head and neck cancer. There are currently no treatments available to patients with head and neck cancer based on genomic insights. This study aims to begin to address the unmet need of patients who present with these poorly understood cancers and to provide a starting point for more detailed investigations into the relationships between cancer genomics and clinical outcomes.

6 Study aim and objectives

6.1 Aim:

To understand the current management of suspected HNSCCUP patients undergoing TBM in the UK, including adequacy of current histology, functional and oncological outcomes, and disease biology.

6.2 Primary objective:

- To establish if step serial sectioning (SSS), compared to conventional histology, improves identification of a primary site in TBM and tonsil specimens in suspected HNSCCUP.

6.3 Secondary objectives:

1. To compare the pick-up rate of primary cancers in TBM specimens between surgical methods (robotic vs laser vs endoscopic).
2. To prospectively evaluate swallowing function and pain scores after TBM.
3. To understand patient views and experiences of undergoing TBM for suspected HNSCCUP.
4. To report time-to-event data for local, regional and distant disease recurrence, and mortality.
5. To assess the molecular makeup of patients with suspected HNSCCUP undergoing TBM.

7 Study design and setting

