12.1 Sample size

No a prior sample size calculation was performed as initial funding limited recruitment to analysis of 60 specimens to undergo SSS. Meta-analysis shows a pickup rate of 58% for this cohort. We anticipate a potential increase pick up rate of around 10%.

- With 60 specimens, the 95% confidence interval boundaries around the pickup rate are +/- 12.6% for 58% and +/-11.4% for 68%.

In anticipation of further funding, our sample size is increased to 100 to give greater confidence in the effect size.

- With 100 specimens, the 95% confidence interval boundaries around the pickup rate are +/- 9.8% for 58% and +/-9.0% for 68%.

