12.2 Study endpoints

For the Primary objective:

- Identification of cancer in the tonsillectomy or TBM specimen on histology.

For the Secondary objectives:

- To compare the pick-up rate of primary cancers in TBM specimens between surgical methods (robotic vs laser vs endoscopic).
 - Identification of cancer in the tonsillectomy or TBM specimen on histology.
 - We anticipate no significant disparity in pick up rate between methods with the limited number of cases in this study.
- To prospectively evaluate swallowing function and pain scores after TBM.
 - We anticipate no significant change in means from pain and MDADI scores between 0 and 6 week questionnaires. Results at 3 weeks are anticipated to be different as still recovering from surgery. Results up to 60 months will evaluate effects of any subsequent treatments and future recovery.
- To understand patient views and experiences of undergoing TBM for suspected HNSCCUP.
 - Qualitative thematic analysis therefore no quantitative end point.
- To report time-to-event data for local, regional and distant disease recurrence, and mortality.
 - Primary emergence rate of around 3% per year.
- To assess the molecular makeup of patients with suspected HNSCCUP undergoing TBM.
 - (Exploratory analysis)

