12.3 Study duration

Recruitment of patients will continue until 100 patients are recruited and undergo TBM. The study duration will be extended as necessary until this target is met across all centres.

The study will remain open until the last patient to be recruited has completed their final 60 month follow-up. Thereafter, end of trial definition will be dependent on resolution of all data queries and completion of database entries in preparation for final statistical analysis and subsequent publication. Once these stages have been reached and the study paperwork is ready for archiving, a 'Declaration of End of Study Form' will be sent to RMH R&D and to the Research Ethics Committee (Health Research Authority) notifying them that the study is now concluded. A summary of the final research report will be provided to the Committee within 12 months of the conclusion of the study. This will report on whether the study achieved its objectives, summarise the main findings, and confirm arrangements for publication or dissemination of the research including any feedback to participants.

Summary of project timings (correct at time of drafting v2.2)

Date	Activity
Dec 2018	First draft of protocol
Jan 2019	Protocol submission to sponsor (CCR)
Feb 2019	CCR review
May 2019	Submission via IRAS
July 2019	REC/HRA approvals
Nov 2019	Opening of first sites
March 2020	COVID-19 disruption
October 2023	Completion of recruitment
October 2028	Completion of 60 month follow up for all patients

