12.4 Analysis methods

Descriptive analysis only is anticipated. The rate of CH and SSS pick up will be reported in the overall specimens and separately in the sub-group of surgical methods with 95% confidence intervals. The pain scores and swallow recovery with MDADI scores will be reported using mean/median and standard deviation or range as appropriate at each time point of 0, 3 weeks, 6 weeks, 3 months, 6 months and 12 months, 24 months, 36 months, 48 months and 60 months. Similarly, score change between time points will be summarized in the same way. The primary and secondary analysis will be done when the complete sample size is recruited and last patient on the study completed all follow-ups.

Molecular data analysis

Detailed description of the molecular analysis methodology is beyond the scope of this protocol.

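### Secondary objective 1 compares pick-up between surgical methods, but the stated analysis gives only one rate and interval per method and never estimates a between-method difference or its precision

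*Protocol*

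**What the plan says.** Protocol section 6.3 lists as the first secondary objective: "To compare the pick-up rate of primary cancers in TBM specimens between surgical methods (robotic vs laser vs endoscopic"). The project summary and section 12.2 repeat it.

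Under that objective, section 12.2 gives an endpoint (cancer found on histology, in tonsil or TBM tissue) and one expectation: "We anticipate no significant disparity in pick up rate between methods with the limited number of cases in this study".

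Section 12.4 opens with "Descriptive analysis only is anticipated". It then says that the pick-up rates for conventional histology (CH) and step serial sectioning (SSS) will be reported overall and "separately in the sub-group of surgical methods with 95% confidence intervals". It names no test, no difference between methods and no interval for a difference.

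Section 12.1 gives precision for the whole sample only. Section 9.6 leaves the surgical technique to each centre's usual practice and records it on the case report form. No number of patients per technique is given anywhere.

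**The concern.** The three statements do not fit together. The objective is a comparison. The expectation in 12.2 is worded in terms of significance. The analysis in 12.4 contains neither a test nor a contrast, only separate summaries of each group.

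The quantity that answers the objective is the difference in pick-up between two methods. Its uncertainty combines the uncertainty of both groups, and no single-group interval displays it. The whole-sample precision in 12.1 does not help, because it is much tighter than anything available for a comparison of subgroups.

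At stake is how the result can be read. Section 12.8 says the study is meant to be the foundation of a possible phase III trial of TBM and SSS, and section 9.6 mentions an affiliated project to standardise the operation. Someone planning either would want to know how large a difference in yield between techniques the data leave open. The stated output does not tell them.

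**Working it through.** **Inputs from the protocol**
- Total: 100 patients (12.3: "Recruitment of patients will continue until 100 patients are recruited and undergo TBM").
- Base pick-up: 58% (12.1: "Meta-analysis shows a pickup rate of 58% for this cohort").
- Expected gain from SSS: about 10 points, giving 68% (12.1).
- Confidence level: 95% (12.4).

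**Assumed, because the protocol gives no figure**
- Patients in the two methods being compared: 33 v 33, 60 v 20 or 20 v 15, with the remainder in the third method.
- A two-sided 5% level wherever significance is discussed.

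**Step 1: the protocol's own precision figures.** Section 12.1 states half-widths of 12.6 and 11.4 points for 60 specimens, and 9.8 and 9.0 for 100, at 58% and 68%. The upper arm of the exact (Clopper-Pearson) interval reproduces all four: 35/60 gives 12.60, 41/60 gives 11.41, 58/100 gives 9.80 and 68/100 gives 8.98. These figures are sound, but each describes a single overall rate.

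**Step 2: precision of a between-method difference.** With the same underlying rate p in both groups, the Wald half-width is

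1.96 × √[p(1 − p)(1/n₁ + 1/n₂)], with p(1 − p) = 0.58 × 0.42 = 0.2436.

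| Split | 0.2436 × (1/n₁ + 1/n₂) | Square root | Half-width |
|---|---|---|---|
| 33 v 33 | 0.01476 | 0.1215 | ±23.8 points |
| 60 v 20 | 0.01624 | 0.1274 | ±25.0 points |
| 20 v 15 | 0.02842 | 0.1686 | ±33.0 points |

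Against ±9.8 points for the whole sample, a between-method difference is about 2.4 to 3.4 times less precise (23.8/9.8 and 33.0/9.8).

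**Step 3: what a null-looking result would mean.** Suppose two methods of 33 patients each yield 19 cancers. The observed difference is zero, and the Newcombe 95% interval is −22.6 to +22.6 points. Identical observed rates would still leave open a difference more than twice the 10-point gain that 12.1 anticipates from SSS.

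**Step 4: chance of significance if a test were run.** The normal approximation is used, with the pooled variance under the null.
- True rates 58% v 38% (20 points): 37% at 33 v 33, 34% at 60 v 20.
- True rates 58% v 28% (30 points): 70% at 33 v 33, 65% at 60 v 20, and 57% at a more uneven 70 v 15.

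A moderate true difference would more often be missed than found. A large one would more often be found than missed.

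**The case against.** The strongest reply is that the sentence in 12.2 is a forecast with its reason attached. It openly admits that cases are few. It is not a hypothesis, a decision rule or a planned conclusion. This stands. A reader might infer that the protocol intends to declare the techniques interchangeable, but nothing in 12.2, 12.4 or 12.8 says so.

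A reader might also infer that a null report is close to certain whatever the truth. That fails twice: 12.4 as written produces no significance statement at all, and if a test were run, a true 30-point difference would reach significance in about 57 to 70% of studies at the splits 33 v 33, 60 v 20 and 70 v 15.

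A third tempting reading is that methods will be judged by whether their separate intervals overlap. Overlap would be a poor rule: 24/33 v 15/33 has overlapping Wilson intervals (56 to 85% and 30 to 62%), although the Newcombe interval for the difference, 4 to 47 points, excludes zero. But 12.4 does not prescribe that rule, and anyone given the counts can compute the difference.

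It can also be said that the choice of contrast and interval method belongs in a statistical analysis plan, and that separate rates are a legitimate minimum for a non-randomised, descriptive objective. In part this is fair. Yet the protocol does not leave the matter open. It fixes a descriptive analysis per method and attaches the language of significance to it. An admission of low precision is a reason to show the interval for the difference.

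**Conclusion.** The concern holds as a mismatch between objective and analysis. Secondary objective 1 asks for a comparison. Section 12.4 supplies no between-method difference, and 12.2 speaks of significance with no test planned. The stated output neither estimates the quantity the objective names nor shows its imprecision.

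The size is about ±24 to ±33 points for a difference between two methods. This rests on assumed group sizes and a common 58% pick-up. The intervals would be wider if one technique is rare: two groups of 15 give ±35.3 points. A non-significant difference would therefore not be evidence of similar yield. The protocol does not claim otherwise.

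The weight is modest. The primary objective, data collection and patients are unaffected.

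**What to change.** In 12.2, replace the sentence about an anticipated lack of significant disparity with a statement that this objective is one of estimation, and that precision will be limited by the number of cases per method.

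In 12.4, add:
- the three pairwise differences in TBM-specimen pick-up (robotic minus laser, robotic minus endoscopic, laser minus endoscopic), for CH and for SSS separately, each with the group sizes and a 95% interval, for example Newcombe's;
- a statement that these contrasts are descriptive and confounded by centre, because technique follows local practice (9.6);
- a statement that a non-significant difference will not be reported as equal yield.

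Naming TBM specimens matters because the endpoint line in 12.2 also admits tonsil tissue, while the objective is confined to TBM.

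The cost is a few sentences and six intervals (three contrasts for each of two histology methods) from data already being collected. The downside is that the wide intervals become visible.

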12.8 Expected Outcomes of the Study

TBM is a relatively new surgical procedure with little data relating to patients experience and recovery from this operation. The pain and MDADI questions will go some way to showing the acceptability of this procedure to patients. It is expected that by 6 weeks the pain and MDADI scores will have returned to near baseline. Most patients will go on to receive radiotherapy to their pharyngeal mucosa, which is known to worsen swallowing function. This data will go some way to clarifying that any subsequent difficulties may not be attributable to the TBM procedure.

Any increased pick up rate resulting from SSS could lead to wider adoption of this process in the management of HNSCCUP. The size of any primary sites identified through SSS over conventional histology will also be recorded and could influence the size of histological levels employed for future TBM and tonsillectomy specimens in the future management of HNSCCUP.

Data from the patient interviews and thematic analysis should help to guide patient goals for any further research in HNSCCUP. Of particular note will be the patients' wishes regarding timing of the tonsillectomy and TBM procedures, which can occur separately, particularly if initial investigation is performed in a peripheral hospital that does not offer TBM. The potential changes in management from identification of primary sites using SSS, and potential for escalation of treatment through the addition of concomitant chemotherapy will also be novel.

Results from the exploratory molecular analysis are expected to give us greater understanding of the molecular make-up of suspected HNSCCUP. Including, but not limited to, how cancers where the primary is identified differ from those primaries that remain occult, and how the cervical disease differs from primary site tissues in the oropharynx.

Results from this prospective observational study will form the foundation of a potential phase III trial investigating the roles of TBM and SSS in management of suspected HNSCCUP. The precise research question is yet to be established.

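### The six-week functional result is worded as no significant change, but the plan has no test and no confidence interval for that change, so it cannot show how large a decline remains possible

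*Protocol*

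**What the plan says.** Four statements in the Protocol bear on this.

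- **Section 12.2**, under the objective on swallowing and pain: "We anticipate no significant change in means from pain and MDADI scores between 0 and 6 week questionnaires". It names no test, interval or margin. It expects the 3-week scores to differ because patients are still recovering from surgery.
- **Section 12.4**: "Descriptive analysis only is anticipated". Pick-up rates are to be given overall and "separately in the sub-group of surgical methods with 95% confidence intervals". Pain and MDADI scores are "reported using mean/median and standard deviation or range as appropriate at each time point", and for change the text says: "Similarly, score change between time points will be summarized in the same way".
- **Section 12.8**: "It is expected that by 6 weeks the pain and MDADI scores will have returned to near baseline". How close counts as near is not defined. After noting that most patients go on to radiotherapy, which is known to worsen swallowing, the section adds: "This data will go some way to clarifying that any subsequent difficulties may not be attributable to the TBM procedure".
- **Section 10.2** places the 6-week assessment immediately before radiotherapy, where radiotherapy is given. For those patients it is the last planned measurement that reflects TBM without radiotherapy.

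**The concern.** Section 12.2 uses the language of a significance test, while Section 12.4 plans no test. The word significant therefore has no defined meaning for this comparison. If it is read as a conventional test, failing to find a difference does not show that patients have recovered. It may only mean that the mean change was imprecisely estimated.

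The planned summaries do not fill the gap. An SD or range describes how much patients differ from one another, not how precisely the mean change is known. The same paragraph specifies confidence intervals for pick-up rates and a different summary for score change. The omission is therefore part of a method that the protocol itself sets out.

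At stake is the attribution argument in Section 12.8. If function at 6 weeks is taken to be back near baseline, later difficulty is more readily put down to radiotherapy. That inference needs an upper limit on the decline that could still be present at 6 weeks, and the plan as written does not report one.

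**Working it through.** **Inputs from the Protocol.** The target is 100 patients (Sections 12.1 and 12.3); funding at first limited the study to 60 specimens (Section 12.1). The comparison is baseline against 6 weeks in the same patients.

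**Inputs not in the Protocol, so assumed.** SD of the individual change: 15 to 20 points for MDADI and 2 to 3 points for a pain item. Complete baseline and 6-week pairs: 60 to 100.

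**The plan's own figures.** Section 12.1 gives half-widths for the pick-up rate only: 12.6 and 11.4 percentage points with 60 specimens, and 9.8 and 9.0 with 100. The upper arm of the exact Clopper-Pearson interval reproduces all four. They are not inputs here. The Protocol states no precision, power or margin for pain or MDADI change.

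**Step 1: precision of the mean change.** Half-width = t(0.975, n−1) × SD / √n.

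- 100 pairs: t/√n = 0.198, so the half-width is 0.198 SD.
- 80 pairs: 0.223 SD.
- 60 pairs: 0.258 SD.

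| Assumed SD of change | 100 pairs | 60 pairs |
|---|---|---|
| MDADI, 15 points | ±3.0 | ±3.9 |
| MDADI, 20 points | ±4.0 | ±5.2 |
| Pain item, 2 points | ±0.4 | ±0.5 |
| Pain item, 3 points | ±0.6 | ±0.8 |

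As an illustration, take an observed mean decline of 2 MDADI points with SD 20 and 60 pairs. The interval runs from a decline of 2 + 5.2 = 7.2 points to a gain of 5.2 − 2 = 3.2 points. The result is not significant, yet a mean decline of about 7 points is not excluded.

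**Step 2: how often a real decline would be non-significant.** Suppose the wording in Section 12.2 meant a two-sided 5% paired t-test. The probability of p > 0.05 comes from the noncentral t distribution with noncentrality d√n, where d is the true mean decline in SD units.

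| True decline | 100 pairs | 80 pairs | 60 pairs |
|---|---|---|---|
| 0.2 SD | 49% | 58% | 67% |
| 0.3 SD | 16% | 25% | 37% |
| 0.4 SD | 2% | 6% | 14% |
| 0.5 SD | 0.1% | 0.7% | 3% |

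With an SD of 15 to 20 points, 0.2 SD is 3 to 4 MDADI points and 0.5 SD is 7.5 to 10. The decline detectable with 80% power is 0.28 SD with 100 pairs and 0.37 SD with 60.

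**Step 3: can a reader recover the interval?** Yes, if the mean change, its SD and the number of pairs are all reported. No, if the median and range are reported. Section 12.4 allows either.

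**The case against.** The strongest reply is that Section 12.2 makes a forecast and sets no rule. The same list forecasts no disparity between surgical methods and an annual rate of primary emergence. The objective is only to evaluate function and pain, and no test of score change is planned anywhere. This stands. A reader might infer that the study will run a test and declare recovery when p exceeds 0.05, but the Protocol does not say so. Misreporting is a risk of the wording and not a planned step.

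A reader might also infer that the plan claims complete recovery by 6 weeks. It does not. Section 12.8 speaks of scores close to baseline and hedges the attribution.

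It can also be said that an interval follows by arithmetic from the mean, SD and number of pairs, and that intervals for secondary summaries are often left to a statistical analysis plan. The first part holds only if the mean and SD are the summary chosen. The second has less force here, because the Protocol itself lays down how change is summarised and specifies intervals for another outcome in the same paragraph.

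Finally, a reader might suspect that the baseline is itself depressed by an earlier tonsillectomy, since Section 12.8 mentions the "timing of the tonsillectomy and TBM procedures, which can occur separately". The documents do not say how often this happens, how long before baseline, or with what effect on scores. No size can be attached to it, and a measurement before TBM is the natural reference for a TBM effect.

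**Conclusion.** The point holds in a limited form. The significance wording in Section 12.2 does not fit the descriptive plan in Section 12.4. The planned summary of change does not show how large a decline remains possible at 6 weeks, although Section 12.8 leans on that comparison.

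Under the assumed SD of 15 to 20 MDADI points and 60 to 100 pairs, the uncertainty is about 3 to 5 points either side of the mean change. Small declines of about 0.2 SD could easily pass as no significant change, and declines of 0.3 SD could do so fairly often. A decline of 0.5 SD would rarely be missed.

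The SDs and pair counts are assumptions. The Protocol gives no smallest important change, so this review does not say whether 3 to 5 points matters to patients. The objective is secondary, and the primary comparison of step serial sectioning with conventional histology is unaffected. The change is worth making because it costs almost nothing and settles what the six-week data can support.

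**What to change.** 1. In Section 12.2, replace the expectation of no significant change with a stated estimate: the paired mean change from baseline to 6 weeks with its 95% confidence interval, for MDADI and for each of the three pain items.
2. In Section 12.4, add that interval and the number of complete pairs to the summary of score change, including where a median and range are also shown.
3. In Section 12.8, word any statement of return to near baseline on the unfavourable end of the interval, against a margin that the sponsor fixes before seeing the data.
4. Optionally, show the change separately for patients whose tonsillectomy preceded the baseline questionnaire, as description only. Section 9.4 already lists surgical history on the case report form.

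The cost is one extra column in a table, a few reworded sentences and the sponsor's choice of a margin. No further patients, visits or questionnaires are needed. The downside is that the recovery statement may have to be more cautious.
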